8.4.2. Method of Detecting Adverse Events and Serious Adverse Events

Care will be taken not to introduce bias when detecting AEs and/or SAEs. Open-ended and non-leading verbal questioning of the participant is the preferred method to inquire about AE occurrences. However, after an occurrence is identified, more specific questions should be asked to obtain adequate information to ensure participant safety by providing proper diagnosis and treatment, and specific, accurate reporting of the event.

8.4.3. Follow-up of Adverse Events and Serious Adverse Events

After the initial AE/SAE report, the investigator is required to proactively follow each participant at subsequent visits/contacts. All SAEs will be followed until resolution, stabilization, the event is otherwise explained, or the participant is lost to follow-up (as defined in [Section 7.3](#)). Further information on follow-up procedures is provided in [Appendix 4](#).

8.4.4. Regulatory Reporting Requirements for Serious Adverse Events

- Prompt notification by the investigator to the sponsor of an SAE is essential so that legal obligations and ethical responsibilities towards the safety of participants and the safety of a study intervention under clinical investigation are met.
- The sponsor has a legal responsibility to notify both the local regulatory authority and other regulatory agencies about the safety of a study intervention under clinical investigation. The sponsor will comply with country-specific regulatory requirements relating to safety reporting to the regulatory authority, IRB/IEC, and investigators.
- An investigator who receives an investigator safety report describing an SAE or other specific safety information (eg, summary or listing of SAEs) from the sponsor will

review and then file it along with the IB and will notify the IRB/IEC, if appropriate according to local requirements.

- Investigator safety reports will be prepared for suspected unexpected serious adverse reactions according to local regulatory requirements and sponsor policy and forwarded to investigators as necessary. The Reference Safety Information for the determination of expectedness of suvecaltamide can be found in the IB.

8.4.5. Pregnancy

- Details of all pregnancies in female participants and, if indicated, female partners of male participants will be collected after the start of study intervention and until 30 days after last study intervention.
- If a pregnancy is reported, the investigator will record pregnancy information on the appropriate form and submit it to the sponsor within 24 hours of learning of the female participant or female partner of male participant (after obtaining the necessary signed informed consent from the female partner) pregnancy.
- While pregnancy itself is not considered to be an AE or SAE, any pregnancy complication or elective termination of a pregnancy for medical reasons will be reported as an AE or SAE.
- Abnormal pregnancy outcomes (eg, spontaneous abortion, fetal death, stillbirth, congenital anomalies, ectopic pregnancy) are considered SAEs and will be reported as such.
- The participant/pregnant female partner will be followed to determine the outcome of the pregnancy. The investigator will collect follow-up information on the participant/pregnant female partner and the neonate, and the information will be forwarded to the sponsor. Neonates will be followed for 6 months following birth.
- Any post-study pregnancy-related SAE considered reasonably related to the study intervention by the investigator will be reported to the sponsor as described in [Section 8.4.4](#). While the investigator is not obligated to actively seek this information in former study participants/pregnant female partner, he or she may learn of an SAE through spontaneous reporting.
- Any female participant who becomes pregnant while participating in the study will be withdrawn from the study.

8.4.6. Adverse Events of Special Interest

The AEOSIs defined for this study are [REDACTED]. Additional information regarding reporting of AEOSIs is provided in [Appendix 4](#).

8.4.7. Other Reportable Experiences: Overdose, Medication Errors, and Misuse

Overdose (defined as any dose administered or received that was higher than the intended dose), medication errors (defined as any unintentional error in the dispensing or administration of the study intervention), and misuse of the study intervention are considered OREs. The method for

completing and transmitting reports of these OREs are provided in [Appendix 4](#). Guidelines for the treatment of overdose are provided in [Section 6.7](#).

If any overdose, medication error, or misuse of the study intervention results in an AE, this must be recorded. If the AE is serious, it must also be reported as described in [Appendix 4](#).

Decisions regarding dose interruptions will be made by the investigator in consultation with the Medical Monitor based on the clinical evaluation of the participant.

8.7. Biomarkers

Biomarkers are not evaluated in this study.

8.8. Immunogenicity Assessments

Immunogenicity assessments are not evaluated in this study.

8.9. Health Economics

Health economics are not evaluated in this study.

9. STATISTICAL CONSIDERATIONS

9.1. Statistical Hypotheses

The null and alternative hypotheses for the primary estimand variable are:

H0: $m_{\text{suvecaltamide}} = m_{\text{control}}$

H1: $m_{\text{suvecaltamide}} \neq m_{\text{control}}$

Specifically, the null hypothesis states that there is no difference in the mean change on the TETRAS composite outcome score (primary estimand) from Baseline to Week 17 between the suvecaltamide and control (placebo) groups. The alternative hypothesis is that the mean change on the TETRAS composite outcome score from Baseline to Week 17 is not equal between the suvecaltamide and control (placebo) groups.

The null and alternative hypotheses for the key secondary estimand variable are:

H0: $p_{\text{suvecaltamide}} = p_{\text{control}}$

H1: $p_{\text{suvecaltamide}} \neq p_{\text{control}}$

Specifically, the null hypothesis states that there is no difference in the proportion of participants who improved by ≥ 1 point on the CGI-S from Baseline to Week 17 between the suvecalcaltamide and control (placebo) groups. The alternative hypothesis is that the proportion of participants who improved by ≥ 1 point on the CGI-S from Baseline to Week 17 is not equal between the suvecalcaltamide and control (placebo) groups.

There are no hypotheses to be tested for the remaining secondary or exploratory endpoints. All safety analyses will be descriptive; no formal statistical testing will be performed.

9.3. Analysis Sets

For the purposes of analysis, the analysis sets are defined as shown in [Table 8](#).

Table 8: Analysis Sets

Participant Analysis Set	Description
Enrolled Analysis Set	All participants who sign the ICF.
Full Analysis Set	All participants who are randomized. Participants will be analyzed according to randomized treatment.
Safety Analysis Set	All participants who are randomized and receive at least 1 dose of study intervention. This analysis set will be used for safety analyses and participants should be summarized according to actual treatment.
Modified ITT Analysis Set	All participants who are randomized, receive at least 1 dose of study intervention, and have baseline and at least 1 non missing evaluable postbaseline TETRAS composite outcome score. Participants will be analyzed according to randomized treatment.

Abbreviations: ICF = Informed Consent Form; ITT = intention to treat; [REDACTED] TETRAS = The Essential Tremor Assessment Rating Scale.

9.4. Statistical Analyses

The SAP will be finalized prior to database lock and will include a more technical and detailed description of the statistical analyses described in this section. This section is a summary of the planned statistical analyses of the most important endpoints, including primary and key secondary endpoints.

9.4.1. General Considerations

In general, results will be summarized by treatment group. Categorical variables will be reported as frequency and proportion. Continuous variables will be reported as the number of participants, mean, SD or SE, median, minimum, and maximum. All summaries, statistical analyses, and individual participant data listings will be completed using Version 9.4 or later of the SAS Statistical Analysis System (SAS Institute, Inc. Cary, NC).

9.4.1.1. Multiplicity Adjustments

A fixed sequence hierarchical testing strategy will be implemented to preserve the family-wise type 1 error rate at the significance level of 0.05. Testing will begin with the comparison of suvecaltamide versus placebo for the primary efficacy variable followed by sequential testing of

the key secondary efficacy variable. The testing procedure will stop when a p-value exceeds 2-sided significance level of 0.05 (see below).

Statistical hypotheses to be tested (in sequential order):

1. Change in TETRAS composite outcome score from Baseline to Week 17, suvecaltamide versus placebo.
2. Proportion of participants who improved by ≥ 1 point on the CGI-S from Baseline to Week 17, suvecaltamide versus placebo.

For the secondary and exploratory endpoints, there will be no control for multiple comparisons.

9.4.1.2. Statistical Methods

Refer to the SAP for a detailed description of statistical methods.

9.4.1.3. Intercurrent Event Strategies

For the primary and key secondary estimands, the following ICEs should be considered:

- Treatment discontinuation due to lack of efficacy or AE; and any other reason including study intervention noncompliance, and other significant protocol deviations.
- Additional/alternative therapies including PRN use of medications to treat tremor, changing background PD treatments, and switching PD treatments.

The ICEs will be handled using 2 approaches:

- As the main approach, treatment policy will be used to address the ICEs. Treatment policy is defined as the effect of the randomized treatment over the study period regardless of whether randomized treatment is continued. Per the treatment policy, data collected (during Efficacy Follow-up Visits) after participants experience a treatment discontinuation ICE will be included for analysis.
- As a supplemental approach, additional analyses of the primary and key secondary estimands will use the hypothetical strategy to address the ICEs. This strategy is defined as the pharmacologic effect of suvecaltamide compared to placebo assuming the intercurrent event did not happen with continuation of randomized treatments for the duration of the study. Analyses will be conducted using data collected at time points that are obtained at or prior to participants discontinuing from randomized treatment and combined with modeled values for post-discontinuation timepoints where the underlying assumptions are considered as appropriate.

In summary, ICEs will be addressed using the treatment policy estimand for the main analysis of the primary and key secondary endpoints and using the hypothetical strategy estimand for supplemental analyses.

9.4.1.4. Pooling of Investigational Centers

Data from all investigational centers will be pooled for presentation of the main results (eg, demographics, efficacy, safety, [REDACTED]). Data may be pooled by region or country as appropriate for exploratory analyses of the primary and key secondary endpoints.

[figure not shown]
9.4.1.5. Dropouts and Missing Data

Every effort will be made to limit premature discontinuation of the study and ascertain completeness of the data collection. Efficacy Follow-up Visits at Weeks 9, 13, and 17 will be conducted as needed for participants who discontinue study intervention but remain in the study to complete scheduled efficacy assessments (see [Section 1.3](#)).

However, missing data caused by reasons defined outside the scope of intercurrent events can still occur (eg, intermittent missing data due to noncompliance). In that case, the MAR assumption will be considered appropriate and missing data will be handled accordingly by MMRM or MI.

[Figure 1](#) provides a flowchart depicting how missing data due to early discontinuation will be addressed for the main analyses of the primary and key secondary efficacy estimands.

Figure 1: Handling of Missing Data Due to Early Discontinuation for the Primary and Key Secondary Efficacy Endpoints

Abbreviations: AE = adverse event; LOE = lack of efficacy; MAR = missing at random; MI = multiple imputation; MMRM = mixed-effect model with repeated measures; MNAR = missing not at random; NRI = non-responder imputation.

Under the main analytical approach, missing data will be assumed to be MAR for participants who do not complete the Efficacy Follow-up Visit(s). The MMRM (for the TETRAS composite outcome score) and MI (for CGI-S response) assume participants with missing data would have efficacy outcomes similar to those participants in their respective study intervention group, randomization stratum, and initial trajectory who completed the study. The MMRM produces an estimate of the treatment effect via restricted maximum likelihood estimation, and a 2-step MI method produces a group of statistical estimates and will be pooled using Rubin's rule.

Under the sensitivity analyses, control-based imputations (for TETRAS composite outcome score) and NRI (for CGI-S response) will be used to treat missing data among participants discontinued due to an AE or lack of efficacy. Tipping-point analyses will be further conducted to assess the robustness of the underlying MAR assumption used in MMRM and MI.

9.4.2. Primary Estimand

The attributes of the primary estimand are listed in [Section 3](#).

For the main estimator analysis, a MMRM will be used to include the change in the TETRAS composite outcome score from Baseline to Weeks 5, 9, 13, and 17. The model will include treatment group, visit, treatment-by-visit interaction, baseline-by-visit interaction, and randomization stratum as fixed effects; baseline TETRAS composite outcome scores as a covariate; and week repeated within each participant as repeated effect. An unstructured variance-covariance matrix will be used to model the correlation among repeated measurements. The Kenward-Roger adjustment of degrees of freedom along with REML will be used to make proper statistical inference. Within-group LS means and the associated 2-sided 95% CIs, treatment difference in LS means and associated 2-sided 95% CIs and p-values will be reported.

Per the treatment policy, the main analyses will include data collected during the Efficacy Follow-up Visits for participants who experience ICEs. However, for participants who experience ICEs and do not attend Efficacy Follow-up Visit(s), missing data will be handled per [Section 9.4.1.5](#).

For sensitivity analysis, control-based imputation methods ([Roger, 2012](#)) will be used to handle missing observations in addition to treatment policy. Details will be further defined in SAP.

For supplementary analysis, a hypothetical strategy will be used to include data points up to the timepoint when a participant experiences an ICE into the MMRM specified above. This will serve as complementary analysis and will ignore observations collected after an ICE.

9.4.3. Secondary Estimand and Endpoints

9.4.3.1. Key Secondary Estimand

The attributes of the secondary estimand are listed in [Section 3](#).

The main estimator will be analyzed using the CMH test adjusting for the stratification factor at randomization (Baseline TETRAS composite score ≤ 17 or > 17). The 2-sided p-values from the CMH test, the adjusted treatment difference in proportion using the weighted average of the treatment differences across the strata with the CMH weights, and the associated 2-sided 95% CIs using a normal approximation to the weighted average will be provided.

Per the treatment policy, the main analyses will include data collected during the Efficacy Follow-up Visits for participants who experience ICEs. However, for participants who experience ICEs and do not attend Efficacy Follow-up Visit(s), missing data for CGI-S will be imputed using a 2-step MI method based on similar participants who remained in the study. Further details will be provided in the SAP.

Sensitivity analyses will be conducted to account for missing data using the NRI method and the tipping point analysis, with further details provided in the SAP.

For supplementary analysis, a hypothetical strategy will be used to include data points up to the timepoint when a participant experiences an ICE into the CMH test specified above. This will serve as a complementary analysis and will ignore observations collected after an ICE; the missing observations will be further imputed using 2-step MI.

9.4.3.2. Secondary Endpoints

Refer to [Section 3](#) for a complete list of other secondary endpoints.

Unless otherwise specified, continuous efficacy endpoints will be analyzed using a MMRM as the primary method. The model will include treatment group, visit, treatment-by-visit interaction, and randomization stratum as fixed effects, and Baseline as a covariate, and participant as a random effect. An unstructured variance-covariance matrix will be used to model the correlation among repeated measurements. The Kenward-Roger adjustment of degrees of freedom along with REML will be used to make proper statistical inference. Within-group LS means and the associated 2-sided 95% CIs, treatment difference in LS means and associated 2-sided 95% CIs, and nominal p-values will be reported.

Binary efficacy endpoints will be analyzed using the CMH test adjusting for the stratification factor at randomization (Baseline TETRAS composite score ≤ 17 or > 17). The 2-sided p-values from the CMH test, the adjusted treatment difference in proportion using the weighted average of the treatment differences across the strata with the CMH weights, along with the associated 2-sided 95% CIs using a normal approximation to the weighted average will be provided.

Per the treatment policy, the main analyses will include data collected during the Efficacy Follow-up Visit(s) for participants who experience ICEs. However, for participants who experience ICEs and do not attend Efficacy Follow-up Visit(s), missing data will be handled per [Section 9.4.1.5](#). No additional sensitivity or supplementary analyses are planned for these secondary endpoints.

For safety endpoints, please refer to [Section 9.4.5](#).

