[REDACTED] SV = Screening Visit; TETRAS-ADL = The Essential Tremor Rating Scale, Activities of Daily Living Subscale; TETRAS-PS = The Essential Tremor Rating Scale, Performance Subscale; W = week; WOCBP = women of childbearing potential.

^a Discontinuation from study intervention does not represent discontinuation from the study. For participants who discontinue study intervention early, every effort should be made to attend Efficacy Follow-up Visits through 17 weeks after the first dose. See [Section 7](#) for additional guidance.

^b If participant discontinues study intervention early (regardless of whether or not he/she continues in the study), he/she will require an E/D Visit and a Safety FU Visit. The E/D Visit should occur as soon as possible following early discontinuation of study intervention. The Safety FU Visit should occur 2 weeks after the E/D visit.

^c Additional onsite clinic visits may be scheduled at any time, including in place of scheduled phone contacts, if required due to local requirements (eg, for study intervention dispensation). If performed in-clinic, urine pregnancy testing should be completed for WOCBP.

^d Clinic visits at Week 1, Week 2, Week 5, Week 9, Week 13, E/D, and Safety FU may be conducted remotely, if required due to the coronavirus 2019 pandemic, and with approval from the Sponsor Medical Monitor. The TETRAS-PS and MDS-UPDRS will not be performed during remote visits [REDACTED]
[REDACTED]

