^a The TETRAS composite outcome score is the sum of modified items 1 to 11 of the TETRAS-ADL and items 6 (6a and 6b) and 7 of the TETRAS-PS. For TETRAS-ADL, each item is modified from 5 response items to 4 response items by collapsing options 0 and 1 together. For TETRAS-PS, each item is modified from 9 response items (due to 0.5 scoring increments) to 4 response items.

Table 6: Secondary and Exploratory Objectives and Endpoints

Objectives	Endpoints
Secondary	
To evaluate the efficacy of suvecaltamide administered once daily for 17 weeks to improve tremor and the functional impairment due to tremor.	
 • Change from Baseline to Week 17 on TETRAS-ADL.^a • Change from Baseline to Week 17 on TETRAS total score (TETRAS-ADL + TETRAS-PS).^a • Proportion of participants who improved (≥ 1 point) from Baseline to Week 17 on the PGI-S. • Proportion of participants who were much improved on the PGI-C at Week 17. • Proportion of participants who were much improved on the CGI-C at Week 17. • Change from Baseline to Week 17 on TETRAS-PS.^a • Change from Baseline to Week 17 on the MDS-UPDRS tremor score (items 2.10, 3.15, 3.16, 3.17, and 3.18).
To evaluate the safety and tolerability of suvecaltamide administered once daily for 17 weeks.	Incidence and severity of AEs as well as evaluation of safety laboratory assessments, vital signs, ECG results, C-SSRS, and QUIP-RS.

Objectives	Endpoints
	█ ██████████
█ █	█ ██████████ █ ██████████ █ ██████████ █ ██████████
█ █ █ █	█ ██████████ █ █ █ ██████████ █ ██████████ █ ██████████

Abbreviations: AUC = area under the plasma concentration-time curve; CGI-C = Clinician's Global Impression of Change; C-SSRS = Columbia Suicide Severity Rating Scale; C_{\max} = concentration at peak; C_{τ} = concentration at trough; ECG = electrocardiogram; █ MDS-UPDRS = Movement Disorder Society Unified Parkinson's Disease Rating Scale; PD = Parkinson's disease; █ PGI-C = Patient's Global Impression of Change; █ PGI-S = Patient's Global Impression of Severity; █ QUIP-RS = Questionnaire for Impulsive-Compulsive Disorders in Parkinson's Disease Rating Scale; █ $t_{1/2}$ = terminal half-life; █ TETRAS-ADL = The Essential Tremor Rating Scale, Activities of Daily Living Subscale; TETRAS-PS = The Essential Tremor Rating Scale, Performance Subscale; T_{\max} = time to maximum concentration.

^a This endpoint uses the unmodified or raw TETRAS score.

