#### 4.4.3. MDS-UPDRS Tremor Score

The MDS-UPDRS consists of 4 parts (Part I through Part IV), with tremor score defined as the sum of selected items (Part II Item 10, Part III Items 15, 16, 17, and 18) on a 4-point ordinal scale ranging from 1 to 4:

- Slight (1)
- Mild (2)
- Moderate (3)
- Severe (4)

MDS-UPDRS tremor score ranges from 0 to 44. Higher scores indicate higher tremor amplitude tremor and more functional impairment due to tremor.

The change from Baseline to Weeks 9, 13 and 17 on the MDS-UPDRS tremor score will be analyzed by MMRM, with model parameters and reporting statistics specified similar to the unmodified TETRAS analysis (Section 4.4.1).

Treatment dropouts and missing observations will be handled as stated in Section 4.1.4.

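### No MDS-UPDRS is planned after the early discontinuation visit, so for participants who stop study drug the tremor-score analysis is close to an on-treatment estimate under a treatment-policy label

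*Protocol*

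**What the plan says.** Protocol Section 3 lists as a secondary endpoint "Change from Baseline to Week 17 on the MDS-UPDRS tremor score (items 2.10, 3.15, 3.16, 3.17, and 3.18". For secondary endpoints, Protocol 9.4.3.2 states: "Per the treatment policy, the main analyses will include data collected during the Efficacy Follow-up Visit(s) for participants who experience ICEs". Its fallback is narrower: "for participants who experience ICEs and do not attend Efficacy Follow-up Visit(s), missing data will be handled per" Section 9.4.1.5, which assumes MAR. That section describes the Efficacy Follow-up Visits at Weeks 9, 13 and 17 as being "for participants who discontinue study intervention but remain in the study to complete scheduled efficacy assessments".

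In Table 4 (Protocol 1.3), the MDS-UPDRS row is marked at Baseline, Weeks 5, 9, 13 and 17, and E/D. The Efficacy Follow-up cell is blank. On the E/D visit, footnote b says: "The E/D Visit should occur as soon as possible following early discontinuation of study intervention".

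SAP Table 7 puts MDS-UPDRS in the same window column as TETRAS and CGI-S, and its note treats Efficacy Follow-up visits as scheduled visits. SAP 4.4.3 fits an MMRM and adds: "Treatment dropouts and missing observations will be handled as stated in Section 4.1.4", again MAR. Protocol 9.4.3.2 and SAP 4.4 plan no sensitivity or supplementary analyses for secondary endpoints. SAP 4.9 records no change on this point.

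On remote visits, footnote d to Table 4 says "Clinic visits at Week 1, Week 2, Week 5, Week 9, Week 13, E/D, and Safety FU may be conducted remotely" under the pandemic provision, and "The TETRAS-PS and MDS-UPDRS will not be performed during remote visits". The table header, however, carries marker d on Efficacy Follow-up and not on E/D.

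**The concern.** The analysis text relies on data that the Schedule does not collect. TETRAS-ADL, TETRAS-PS, CGI-S, CGI-C, PGI-S and PGI-C are all marked at Efficacy Follow-up; MDS-UPDRS is not. A participant who stops drug and attends every follow-up visit contributes observed off-drug values to the other secondary endpoints but none to the tremor score after E/D.

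The fallback in Protocol 9.4.3.2 is written for participants who stay away from follow-up. It does not describe those who attend but have no MDS-UPDRS taken by design. In practice both groups are handled under MAR. For the tremor score, discontinuation is then treated much as Protocol 9.4.1.3 and SAP 4.1.3 define the hypothetical strategy, while the result carries the treatment-policy label.

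If benefit fades after stopping, the reported effect is larger than the treatment-policy effect. Stopping on the active arm is enough to cause this; it need not be more frequent than on placebo. No planned analysis would show it. The tremor score is also the only listed primary or secondary efficacy endpoint built on a Parkinson's disease scale, and Protocol 8.2 acknowledges that the TETRAS has not been validated in that population.

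**Working it through.** **1. Schedule marks (Protocol Table 4), read field by field against the header**

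| Scale | Marked visits |
|---|---|
| TETRAS-PS | Screening, Baseline, W5, W9, W13, W17, Efficacy FU, E/D |
| CGI-C | W9, W13, W17, Efficacy FU, E/D |
| MDS-UPDRS | Baseline, W5, W9, W13, W17, E/D |

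The MDS-UPDRS row has two marks fewer than TETRAS-PS: Screening and Efficacy Follow-up.

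**2. What data remain after stopping.** The E/D visit gives one MDS-UPDRS close to the stop. SAP 4.1.2 and Table 7 map it to a window: Days 1–48 to Week 5, 49–76 to Week 9, 77–104 to Week 13, and from Day 105 to Week 17. Only a stop from about Day 105 can therefore supply a Week 17 value. For earlier stops, Week 17 has no planned value.

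**3. What the planned 20% is.** The documents give no figure for the tremor score. The nearest is the dropout rate in Protocol Table 3 and SAP Section 5: 160 × (1 − 0.20) = 128 completing Week 17 assessments, or 64 of 80 per arm. Those dropouts lack Week 17 data on every scale. The share that matters here is participants who stop drug and attend follow-up, and it has to be assumed.

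**4. Size.** Let d be the on-treatment effect, f the share of the active arm who stop drug and attend follow-up, and k the fraction of benefit lost after stopping. The treatment-policy effect is about (1 − f·k)·d. Assume MAR returns about d. The ratio of reported to treatment-policy effect is then 1/(1 − f·k).

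| f (number of 80) | k = 1 | k = 0.5 |
|---|---|---|
| 5% (4) | 1/0.95 = 1.05 | 1/0.975 = 1.03 |
| 10% (8) | 1/0.90 = 1.11 | 1/0.95 = 1.05 |
| 20% (16) | 1/0.80 = 1.25 | 1/0.90 = 1.11 |

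With k = 0 the ratio is 1.

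**5. Check by simulation.** Assumptions: on-treatment effect 1.00; the same non-informative stopping in both arms after Week 5, 9 or 13; correlation 0.7 between adjacent visits; no E/D values used. The MAR estimate stayed at about 1.00. With full loss, the treatment-policy value was 0.91 at 10% stopping and 0.81 at 20%. With half lost, it was 0.94 and 0.89. With none lost, the two agreed. This matches the formula.

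**6. Marker d.** On the header's reading, a 17-week Efficacy Follow-up visit could be remote. TETRAS-PS items 6 and 7 would then be missing and no TETRAS composite could be formed, whereas the on-treatment Week 17 visit carries no remote marker. On the footnote's reading, the E/D visit could be remote, and the single MDS-UPDRS near stopping would be lost.

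**The case against.** The strongest reply is that Protocol 9.4.3.2 promises to include data that are collected, not to collect every scale, and that Section 9.4.1.5 ties follow-up to the scheduled assessments. Formal estimands exist only for the primary and key secondary endpoints. This explains how the gap arose but does not remove it: 9.4.3.2 names treatment policy for these endpoints without excepting the tremor score, and SAP Table 7 treats follow-up visits as scheduled for it.

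Four stronger readings are tempting, and the documents do not support them.

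- *The analysis cannot be done.* The MMRM can be fitted. Additional or alternative therapy in participants still on drug is followed at the regular visits, so treatment policy works for that event as written.
- *There are no data after discontinuation.* The E/D visit supplies one value, and a late one can count as Week 17.
- *The planned 20% dropout gives the size.* Those participants are missing on every scale, so the other endpoints also rest on MAR for them, and adding MDS-UPDRS at follow-up would recover nothing. If 20% stopped drug and half of them attended, f would be 10% and the ratio at most about 1.11.
- *This is the only endpoint on a Parkinson's disease instrument.* SAP 4.5.2 also analyses MDS-UPDRS Parts I–IV and the total as exploratory endpoints, and others are redacted.

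On the remote-visit marker, it is fair to say that the footnote text omits Efficacy Follow-up, that part of the footnote is redacted, and that the provision needs Sponsor Medical Monitor approval. The two visit lists still disagree.

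**Conclusion.** The point holds in a limited form. For participants who stop drug and attend follow-up, the plan provides no tremor score after E/D. The Week 17 estimate rests on MAR for them and approximates a hypothetical effect for treatment discontinuation, without being labelled so.

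The overstatement is about 1.03 to 1.25 times over the assumed range: f from 5% to 20%, and half or all of the benefit lost. The 20% row is an upper illustration, not an estimate. These figures assume that MAR returns the on-treatment effect and give no weight to E/D values, which would soften them somewhat.

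The consequence is contained. The endpoint lies outside the alpha-controlled sequence and its p-value is nominal. The primary and key secondary scales are marked at Efficacy Follow-up, so this gap does not touch them. The exploratory MDS-UPDRS scores share it. The marker mismatch is a separate, smaller matter. It could cost a primary endpoint value, but only for a participant whose 17-week follow-up visit is held remotely.

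The blank cell should be confirmed on the published page, because marks in a few other rows of Table 4 (pregnancy test, urine drug screen, QUIP-RS) look displaced in the text version. The MDS-UPDRS row itself aligns fully with the header.

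**What to change.** Do one of the following.

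(a) Mark MDS-UPDRS in the Efficacy Follow-up column of Table 4, at least items 2.10 and 3.15 to 3.18. The cost is some minutes at visits already attended; the full scale takes about 30 minutes (Protocol 8.2.7).

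(b) State in Protocol 9.4.3.2 and SAP 4.4.3 that no MDS-UPDRS is planned after the E/D visit; that the tremor score is therefore estimated under the hypothetical strategy for treatment discontinuation only; and that treatment policy is kept for additional or alternative therapy, as SAP 4.1.3 already separates them. Label the result this way in the report. This costs wording only and remains possible if data collection has ended. The limit to treatment discontinuation matters: Protocol 9.4.2 describes the hypothetical analysis as ignoring observations after any intercurrent event, which would discard valid on-treatment data.

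Under (b), align the note to SAP Table 7 so that it does not imply follow-up data for MDS-UPDRS.

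Separately, reconcile the Table 4 header with footnote d on which visits may be remote, and state what that means for the TETRAS composite at the 17-week Efficacy Follow-up visit and for MDS-UPDRS at E/D. This is an editorial correction.
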